4.3. Study Early Termination

- This study can be temporally or definitively terminated based on the Sponsor, Principal Investigator or Ethics and Investigation Committee or Investigation Committee's decision, according the Ministry of Health guidelines.
- Causes may be different, among others the frequency and type of adverse events which make a considerable number of subjects to take the decision of terminating the study; new drug's information which states that the subjects' safety or study conduct might be affected; or by reasoned decision by the Ethics and Investigation Committee, Investigation Committee and the Ministry of Health.
- In the event of temporary or early termination, study subjects will be immediately informed and an appointment will be scheduled to inform them about the final decision about the study course. For definitive termination, the Principal Investigator will inform this decision to the study subjects and will perform the termination procedures.

- If the decision is taken by the Sponsor or the Principal Investigator, they should document the decision and inform in writing, with a detailed explanation about the temporary or definitive termination, to the Ethics and Investigation Committee, to the Investigation Committee and to the Ministry of Health.
- Study drugs will be kept safely and will be disposed (return or storage) as agreed with the Sponsor.

4.4. Study Procedures

4.4.1. Subjects Screening

Once the informed consent form is signed, subjects' eligibility will be checked according to the inclusion and exclusion criteria. Confirmation of the medical chart and its update will be made according to the standard operating procedure, code: PPD , at the

PPD If the subject already has a medical chart, the medical history will only be updated.

Subjects should have:

- Laboratory tests within 30 days prior to the study start-up.
- Electrocardiogram within 30 days prior to the study start-up.

4.4.2. Study Periods

To confirm that the subject is still a suitable candidate for the study at the entrance of each period, a clinical assessment consisting of interrogation by apparatus and systems with a physical exam and an electrocardiogram will be carried out. Urine samples will be taken for abuse drugs screening; for women, a blood sample will be taken for the pregnancy tests. In addition, a breath alcohol test will be done.

At the end of each period, a clinical assessment consisting of an interrogation, physical exam, vital signs measurement and adverse events follow-up will be done.

Subjects should inform to the medical staff in charge of the study conduct about any symptom they have. Likewise, the medical staff will enquire in each period to the subjects about symptoms since the first period and following the dosing. Should they report any, the medical staff should provide treatment to the subject and notes to the appropriate documents will be made.

Prior to the dosing, blood pressure (seated position), pulse, respiratory frequency and temperature will be measured to each subject. These values should be within the normal ranges (SBP between 80 and 129 mmHg and DBP between 50 and 80 mmHg) in order the subjects keep on participating in the study. Same measurements will be taken in every shift following the dosing in each phase. Vital signs will be taken as shown in Table No. 3.

TABLE No. 3
Vital Signs Record

First Period	Second Period
Admission	Admission
Pre-dose	Pre-dose
Morning shift (2 to 3 h after administration)	Morning shift (2 to 3 h after administration)
Evening shift (6 to 8 h after administration)	Evening shift (6 to 8 h after administration)
Night shift (11 to 13 h after administration)	Night shift (11 to 13 h after administration)
Discharge (23 to 24 h after administration)	Discharge (23 to 24 h after administration)
Ambulatory sample (36 and 48 hours)	Ambulatory sample (36 and 48 hours)

If any subject has clinically significant changes, out of the normal ranges, in his/her blood pressure and pulse during post-dose confinement, he/she will be closely checked by the medical staff and appropriate supporting measures will be taken according to the his/her condition until resolution. Should these changes persist, his/her participation in the study will be checked by the Principal Investigator.

Due to operations issues, the Principal Investigator may change the study start-up (from the study drug intake) in 1 hour, if it does not affect the study result.

4.4.2.1. *Drugs to be given*

Drugs to be given to the subjects in each of the study visits will be given by the study Sponsor.

- International non-proprietary name: Levothyroxine Sodium.
- Reference drug: Eutirox® (approved formulation).
 - Dosage form: tablets.
 - Qualitative-quantitative formula: each tablet contains levothyroxine sodium 200 µg.
 - Expiry date: The expiry date must not be before the end of the study.
 - Sanitary approval number: 297M89, SSA IV.
 - Manufacturer: Merck, S. A. de C. V.
 - Distributor: Merck, S.A. de C.V.
 - Marketing Authorization Holder: Merck, S.A. de C.V.
- Test drug: Eutirox® (new formulation).
 - Dosage form: tablets.
 - Qualitative-quantitative formula: each tablet contains levothyroxine sodium 200 µg.
 - Expiry date: The expiry date must not be before the end of the study.

- Manufacturer: Merck, S. A. de C. V.
- Distributor: Merck, S. A. de C. V.
- ✚ Dose to be given: 600 µg (3 tablets of 200 µg), orally.

4.4.2.2. *First Treatment Period*

- ✚ Admission in the afternoon of the day before dosing (approximately at 3pm).
- ✚ Dinner at least 10 hours before the dosing.
- ✚ Catheter insertion (as chosen).

First Day:

- ✚ At 06:00 h, grooming and intake of 250 mL of water.
- ✚ Between 06:30 and 07:30 h, catheter insertion.
- ✚ As per 07:30 h, first pre-dose sample (- 0.50 h); as per 07:45 h, second pre-dose sample (-0.25 h); and as per 07:55 h, third pre-dose sample (0 h).
- ✚ As per 08:00 h, study drug or reference drug dosing with 250 mL of room temperature water, according to the standard operating procedure, code: PPD [REDACTED]
- ✚ From 08:30 to 20:00 h, sampling according to the schedule.
- ✚ As per 12:00 h, breakfast.
- ✚ As per 16:00 h, lunch.
- ✚ As per 21:00 h, dinner.

Second Day:

- ✚ At 08:00 horas, 24.0 h sampling.
- ✚ Approximately at 10:00 h, discharge from the clinic.
- ✚ At 20:00 h, 36.0 h ambulatory sampling.

Third Day:

- ✚ At 08:00 h, 48.0 h ambulatory sampling.
- ✚ Approximately at 10:00 h, temporary discharge with open appointment.

4.4.2.3. *Wash-out Period*

Wash-out period length is of 35 days starting at the drug's dosing in the previous period. It is intended to remove the previous dose before giving the next one and fulfills the criterion of the NOM-177-SSA1-2013 of at least 7 half-lives for the study drug.

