1.2.2. Levothyroxine pharmacokinetic parameters

TABLE No. 1

No.	Doses	C _{max}	t _{max} (h)	t _½ (h)	AUC _{0-∞}	Reference
1)	600 µg*	11.58 (2.10) µg/dL	2.50 (4.50)	403.84 (16850.26)	14447.11 (36474.98) µg·h/dL	Abib et al. , (2010)
2)	600 µg**	11.53 (2.40) µg/dL	2.00 (23.02)	348.30 (6309.87)	10679.17 (17326.22) µg·h/dL	Abib et al. , (2010)
3)	600 µg*	112.0 ± 17.3 ng/ml	3.9 ± 1.6	ND	◊ 4359.3 ± 619.3 ng h/ml	Koytchev & Lauschner, (2004)
4)	600 µg**	113.4 ± 18.5 ng/ml	4.6 ± 2.0	ND	◊ 4463.8 ± 694.7 ng h/ml	Koytchev & Lauschner, (2004)

1) and 2) Data reported as mean (standard deviation); 3) and 4) Data reported as mean ± standard deviation; * Test drug; ** Reference drug; ◊ AUC_{0-48h}; NA, not available.

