1.2.2.4. Excretion

Levothyroxine's elimination is produced by conjugation with glucuronic and sulfuric acid, and excretion in the bile. Thyroid hormones release by means of bacterial hydrolysis in the bowel and partial re-absorption lead to enterohepatic circulation. Approximately 20 - 40 % of thyroxine is cleared in the feces (Koytchev & Lauschner, 2004).

T4 elimination half-life is approximately 6.2 days in healthy volunteers, meanwhile T3 half-life is of approximately 1 day (*Guidance to Establish the Interchangeability of Oral Solid Drugs Containing Levothyroxine Sodium, COFEPRIS, 2017*).

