4.1. Experimental design and study plan

Single dose design will be used with 44 subjects in fasting state, two periods, two sequences, open-label, crossed in scheme blocks A-B and B-A, randomized, longitudinal, comparative and prospective, with a 35-day wash-out period between the two study periods. Treatment groups will be balanced, with the same number of subjects who will be randomly assigned to the study drug sequences of administration.

All data from participant subjects should be analyzed and included in the statistical analysis, if the fulfill with the established criteria.

Selection period (Screening)	Clinical phase			
	Period 1	Washout	Period 2	Clinical monitoring End of Study
30 to 2 days before the start of Period 1	From approx.12 hours pre-dose until 48 h sampling post- dose	At least 35 days	From approx. 12 hours pre-dose until 48 h sampling post- dose	At least 14 days after the dose in period 2

Subjects will be randomized to one of the 2 sequences by a randomization plan completed before first dosing

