4.4.3. Blood sampling schedule

Clinical Stage

NUMBER OF SUBJECTS:	44	SEX:	Male or female
BIOLOGICAL MATRIX:	Serum	DOSAGE FORM:	Tablets
PHARMACEUTICAL FORM:	Levothyroxine sodium 200 µg	DOSES AND NO. OF UNITS:	200 µg (3 tablets)
WASH-OUT PERIOD:	35 days	ANTICOAGULANT:	Does not apply
BLOOD VOLUME EXTRACTED PER SAMPLE:	10 mL	TOTAL OF SAMPLES PER SUBJECT IN EACH PERIOD:	26

Sampling time interval

Stage	Sample	Time	Unit
Pre-dose	01	- 0.50	h
Pre-dose	02	- 0.25	h
Pre-dose	03	0.00	h
A	04	0.50	h
A	05	1.00	h
A	06	1.50	h
A	07	2.00	h
A	08	2.50	h
~ C _{max}	09	3.00	h
~ C _{max}	10	3.25	h
~ C _{max}	11	3.50	h
~ C _{max}	12	3.75	h
~ C _{max}	13	4.00	h
~ C _{max}	14	4.25	h
~ C _{max}	15	4.50	h
~ C _{max}	16	4.75	h
~ C _{max}	17	5.00	h
E	18	5.50	h
E	19	6.00	h
E	20	6.50	h
E	21	8.00	h
E	22	10.00	h
E	23	12.00	h
E	24	24.00	h
E	25	36.00	h
E	26	48.00	h

Total number of samples			
No. of cases	Samples	Periods	Total
44	26	2	2,288
Diet			
Standardized by the clinical unit			

Each subject will have a participation of 64 hours approximately (approximately 43 hours confined with outpatient follow-up for the 36 and 48-h samples) for each of the periods, with a wash-out period of 35 days, starting as per the drug's intake in the 1st period, according to the following schedule:

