4.5.5. Variable Assessment Periods

For the study conduct the following periods have been planned:

- **Screening:** within the 30 days prior to the dosing.
- **First period of the study:** from the 16.00 hours prior to the first dose and at least 48.00 hours post-dose.
- **Wash-out period:** 35 days between each dose.
- **Second period of the study:** from the 16.00 hours prior to the second dose and at least 48.00 hours post-dose.
- **Study withdrawal:** following the 48.00-hour sampling in the second period.

- ✚ **Follow-up of adverse events:** adverse events occurring in a 14-day period following the dosing in the second period will be reported. Adverse events that were presented during the follow-up period and continued unresolved in the final visit, should be followed until resolved are no longer considered as clinically relevant or can be explained.
- ✚ **Final Visit:** 14 days after last administration of the study product.
- ✚ **End of study:** The study will end when the last subject has been subjected to the activities described in the final visit (section 4.4.2.6.) and the laboratory or cabinet findings or adverse events, if detected, have been explained and closed by the investigator.

For the wash-out period - drug's elimination - time when the subjects are out of the clinic, general directions will be given to each subject. They include specific information about feeding, restriction of drugs and overall care.

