5.3. Approval by Regulatory Authorities

This study will be carried out according to the provisions of the regulations set forth in the NOM-177-SSA1-2013 which states the tests and procedures for proving that a drug is interchangeable and the requirements which third parties performing interchangeability tests should fulfill; the requirements for conducting biocomparability studies; requirements for authorized third parties, research centers or hospital institutions conducting biocomparability tests, as well as the NOM-012-SSA3-2012 which states the criteria for conducting research project for human beings health.

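### Section 4.4.2.3 says the 35-day wash-out covers at least 7 half-lives, but at the protocol's own T4 half-life of about 6.2 days it covers about 5.6

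*Protocol*

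**What the plan says.** - Section 4.4.2.3 fixes the wash-out at 35 days, starting at the previous period's dose, and says that this "fulfills the criterion of the NOM-177-SSA1-2013 of at least 7 half-lives for the study drug".
- Section 1.2.2.4 states: "T4 elimination half-life is approximately 6.2 days in healthy volunteers". The same sentence gives about 1 day for T3.
- The count is from dose to dose elsewhere too: section 4.4.3 has "with a wash-out period of 35 days, starting as per the drug's intake in the 1st period" and section 4.5.5 has "35 days between each dose".
- The design table in section 4.1 has "At least 35 days".
- Sections 4.4.4, 4.5.6 (Table 5) and 12.2 place the doses on Days 1 and 36. Footnotes 2 and 6 of Appendix 12.1 suggest TD1 and TD35 instead.
- Section 5.3 commits the study to the same standard: "This study will be carried out according to the provisions of the regulations set forth in the NOM-177-SSA1-2013".
- The primary endpoints are baseline-adjusted Cmax and AUC of T4 (Table 2). The adjustment subtracts the mean of the pre-dose levels (section 7.2).

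**The concern.** A crossover relies on the first dose having largely gone before the second is given. The protocol supports its wash-out with one numerical claim, that 35 days is at least seven half-lives, and attributes the criterion to a standard it undertakes to follow. A reader who sets section 1.2.2.4 beside section 4.4.2.3 can test that claim with one division, and it fails. What is at stake is the accuracy of a stated design property and of a compliance statement that an ethics committee or the authority may rely on. Whether carry-over could also distort the bioequivalence result is a separate question, checked below.

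**Working it through.** **Inputs.** Wash-out 35 days, dose to dose (4.4.2.3, 4.4.3, 4.5.5). T4 half-life about 6.2 days (1.2.2.4). Claimed multiple at least 7 (4.4.2.3). AUC window 48 h, so T = 2 days (4.4.3).

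**1. The protocol's own figure.** Half-lives covered = wash-out / half-life = 35 / 6.2 = 5.65. The stated figure of at least 7 is not reproduced.
- Days needed: 7 × 6.2 = 43.4. Shortfall: 43.4 − 35 = 8.4 days.
- Break-even half-life: 35 / 7 = 5.0 days. The protocol gives no T4 half-life this short.
- Rounding of the 6.2: 6.15 to 6.25 days gives 5.69 to 5.60 half-lives.
- Calendar: doses on Days 1 and 36 are 35 days apart. Doses on TD1 and TD35 would be 34 days apart, and 34 / 6.2 = 5.5, so the Appendix 12.1 reading does not help.

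**2. How much drug is left.** Assume one compartment, first-order decay and immediate absorption. Residual fraction r = 2^(−35/6.2) = 0.0200, or 2.0% of the period-1 dose. After seven half-lives it would be 2^(−7) = 0.0078, or 0.8%.

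**3. What baseline subtraction does to it in the AUC.** Let k = ln 2 / 6.2 = 0.1118 per day.
- A unit dose contributes A = (1 − exp(−kT)) / k = (1 − 0.7996) / 0.1118 = 1.79 over the 2-day window.
- The residual contributes r × A to period-2 AUC. Subtracting the constant pre-dose mean takes off r × T.
- T / A = 2 / 1.79 = 1.12, so the subtraction takes off about 112% of what the residual adds. It slightly over-corrects.
- Net error relative to the dose's own AUC: r(T − A) / A = 0.00232, or about 0.23%.

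**4. Effect on the test/reference AUC ratio.** Let R be the true ratio and d = 0.00232. When test follows reference, the observed ratio is R − d. When reference follows test, it is R / (1 − dR). The 2×2 estimate is the exponential of the mean of the two logs.

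| True R | Bias in the estimated ratio |
|---|---|
| 0.95 | −0.012% |
| 1.05 | +0.011% |
| 0.80 | −0.052% |
| 1.25 | +0.052% |

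The errors in the two sequences nearly cancel because both products leave a similar residual.

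**The case against.** **The strongest defence is that nothing material follows.** The endpoints are baseline-adjusted, the residual is about 2%, and the ratio bias is a few hundredths of a percent. This stands. It limits the point to the statement but does not make the statement true.

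**The wording in section 4.1 is only a minimum.** A longer interval would be compatible with that table. But a minimum of 35 does not require 43.4, and the other sections give a flat 35 days.

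**The T3 half-life of about 1 day would satisfy the criterion.** The sentence, however, refers to the study drug, and the endpoints are T4.

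**The multiple may simply be misquoted.** The text of the standard is not at hand, so the 7 rather than the 35 may be the wrong element. This also stands, and it is why the check of the clause belongs in the fix. For the same reason, a reader might infer that the study breaches the standard, but the documents do not support that. They show only that the protocol does not meet the criterion as it words it.

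**A reader might also infer serious carry-over from Table 1.** It lists half-lives of 348.30 h and 403.84 h, or 14.5 and 16.8 days. The standard deviations beside them are 6309.87 h and 16850.26 h, about 18 and 42 times the means (6309.87 / 348.30 = 18.1; 16850.26 / 403.84 = 41.7), and the protocol does not say whether the values are baseline-corrected. They say almost nothing about how fast an exogenous dose decays and cannot support a carry-over estimate.

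**Conclusion.** The sentence in section 4.4.2.3 is wrong as written. On the protocol's own half-life the wash-out covers about 5.6 half-lives, not at least 7, and neither rounding, the way the days are counted, nor any other T4 half-life usable for this purpose rescues it. This is an internal inconsistency in a stated design property and in the compliance claim attached to it. It should be corrected.

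It is not evidence that the bioequivalence result is at risk. The AUC ratio bias is about 0.01% at a 5% difference and about 0.05% at the margins. Those figures assume a 6.2-day half-life, one compartment, first-order decay, immediate absorption and subtraction of the same-period pre-dose mean. The 5.65 rests only on the two numbers in the protocol.

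**What to change.** Correct the sentence in section 4.4.2.3, for example: *The 35-day wash-out is about 5.6 half-lives of T4 (6.2 days); by first-order decay about 2% of the previous dose may remain, and the same-period pre-dose baseline correction leaves an AUC error of about 0.2%.*

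Also check the multiple in the standard:
- **If 7 was misquoted,** give the right multiple and keep 35 days. Cost: one sentence.
- **If 7 is required and 35 days is kept,** state and justify the departure. Cost: the sentence and a short justification, for which the figures above can serve.
- **If 7 is required and the wash-out is lengthened,** use at least 44 days (44 / 6.2 = 7.1 half-lives). With the first dose on Day 1, the second falls on Day 45, and the period-2 and final-visit days shift accordingly. Cost: 9 more days per subject.

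No option adds samples or visits. Given the size of the bias, lengthening is warranted only if the standard requires it. In the same edit, align the TD34 and TD35 references in Appendix 12.1 with the day numbering used elsewhere.

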4.4.2.4. Second Treatment Period

- ✚ Admission the afternoon of the day before dosing (approximately at 3pm).
- ✚ Dinner at least 10 h before the dosing.
- ✚ Catheter insertion (as chosen).

First day:

- ✚ At 06:00 h, grooming and intake of 250 mL of water.
- ✚ Between 06:30 and 07:30 h, catheter insertion.
- ✚ As per 07:30 h, first pre-dose sample (- 0.50 h); as per 07:45 h, second pre-dose sample (-0.25 h); and as per 07:55 h, third pre-dose sample (0 h).
- ✚ As per 08:00 h, study drug or reference drug dosing with 250 mL of room temperature water, according to the standard operating procedure, code: PPD
- ✚ From 08:30 to 20:00 h, sampling according to the schedule.
- ✚ As per 12:00 h, breakfast.
- ✚ As per 16:00 h, lunch.
- ✚ As per 21:00 h, dinner.

Second Day:

- ✚ At 08:00 horas, 24.0 h sampling.
- ✚ Approximately at 10:00 h, discharge from the clinic.
- ✚ At 20:00 h, 36.0 h ambulatory sampling.

Third Day:

- ✚ At 08:00 h, 48.0 h ambulatory sampling.
- ✚ Approximately at 10:00 h, temporary discharge with open appointment.

4.4.2.5. Clinical Follow-up

All study subjects will be followed-up in an outpatient basis, as per the last drug's dosing, with open appointment or telephone contact as per the Investigator's opinion, for 14 days after last administration.

4.4.2.6. Final visit

14 days after the last administration, the subjects will be cited for their final visit in which the following evaluations will be made:

- Sampling for clinical laboratory: equal to the tests carried out in the screening.
- Control electrocardiogram.
- Medical review: will include directed interrogation (including AEs) and physical examination.

4.4.2. 7. End of the study

Any clinically relevant deviation from the initial findings for all subjects should be monitored until they have returned to normal, are no longer considered clinically relevant or can be explained.

Adverse events that were presented during the follow-up period and continued unresolved in the final visit, should be followed until resolved, are no longer considered clinically relevant or can be explained.

The study will end when the last subject has been subjected to the activities described in the final visit and the laboratory or cabinet findings or adverse events, if detected, have been explained and closed by the investigator.

CONFIDENTIAL

4.4.3. Blood sampling schedule

Clinical Stage

NUMBER OF SUBJECTS:	44	SEX:	Male or female
BIOLOGICAL MATRIX:	Serum	DOSAGE FORM:	Tablets
PHARMACEUTICAL FORM:	Levothyroxine sodium 200 µg	DOSES AND NO. OF UNITS:	200 µg (3 tablets)
WASH-OUT PERIOD:	35 days	ANTICOAGULANT:	Does not apply
BLOOD VOLUME EXTRACTED PER SAMPLE:	10 mL	TOTAL OF SAMPLES PER SUBJECT IN EACH PERIOD:	26

Sampling time interval

Stage	Sample	Time	Unit
Pre-dose	01	- 0.50	h
Pre-dose	02	- 0.25	h
Pre-dose	03	0.00	h
A	04	0.50	h
A	05	1.00	h
A	06	1.50	h
A	07	2.00	h
A	08	2.50	h
~ C _{max}	09	3.00	h
~ C _{max}	10	3.25	h
~ C _{max}	11	3.50	h
~ C _{max}	12	3.75	h
~ C _{max}	13	4.00	h
~ C _{max}	14	4.25	h
~ C _{max}	15	4.50	h
~ C _{max}	16	4.75	h
~ C _{max}	17	5.00	h
E	18	5.50	h
E	19	6.00	h
E	20	6.50	h
E	21	8.00	h
E	22	10.00	h
E	23	12.00	h
E	24	24.00	h
E	25	36.00	h
E	26	48.00	h

Total number of samples			
No. of cases	Samples	Periods	Total
44	26	2	2,288
Diet			
Standardized by the clinical unit			

Each subject will have a participation of 64 hours approximately (approximately 43 hours confined with outpatient follow-up for the 36 and 48-h samples) for each of the periods, with a wash-out period of 35 days, starting as per the drug's intake in the 1st period, according to the following schedule:

4.4.4. Schedule

Pre-clinical Stage	Clinical Stage			Post-Clinical Stage
Activity from day -120 to 0	Day	Time	Activity	Activity as per day 38
▪ Protocol's elaboration.	0	As per 15:00 h	Admission.	
▪ Preparation of the non-pregnancy letter, summary, schedule, ICF, and CRF.	VISIT 1			
▪ Protocol's approval.	01	06:00 h	Intake of 250 mL of water.	▪ Subjects' clinical follow-up.
		06:30 h	Catheter insertion.	▪ CRF close-out.
		07:30 - 07:55 h	Pre-dose sampling.	▪ Delivery to the Analytical Unit.
		08:00 h	Drug intake.	▪ Clinical Report elaboration.
		08:30 h	Start of sampling (post-dose)	▪ Analytical stage.
▪ Approval by the Ethics and Investigation Committee and Investigation Committee.	02	08:00 h	24.0-h sampling	▪ Final report.
		Approximately at 10:00 h	Discharge from the Clinical Unit	▪ Study close-out.
		20:00 h	36.0-h ambulatory sampling	▪ Approval request for the biological samples disposal.
		08:00 h	48.0-h ambulatory sampling	
		Approximately 10:00 h	Temporal discharge, open appointment	
Wash-out Period – 35 days				
▪ Filing at the COFEPRIS.	35	As per 15:00 h	Admission	
▪ COFEPRIS approval.	VISIT 2			
▪ Drug's receipt.	36	06:00 h	Intake of 250 mL of water	
▪ Planning.		06:30 h	Catheter insertion	
▪ Subjects screening.		07:30 – 07:55 h	Pre-dose sampling	
		08:00 h	Drug intake	
		08:30 h	Sampling start (post-dose)	
	37	08:00 h	24.0-h sampling	
		Approximately at 10:00 h	Discharge from the Clinical Unit	
		20:00 h	36.0-h ambulatory sampling	
		08:00 h	48.0-h ambulatory sampling	
		Approximately at 10:00 h	Definitive discharge, open appointment.	

